2.5.6.2 Drug Information

2.5.6.2.1 Treosulfan

Treosulfan will be supplied to investigators by Medac GmbH, Hamburg Germany under an IND held by Fred Hutchinson Cancer Center. The drug will be delivered to each participating center's investigational drug pharmacy as a clinical investigational product with a study-specific label on the glass vial, as approved by the FDA.

Information regarding the physical, chemical, and pharmaceutical properties for Treosulfan, as well as formulations, storage and handling, and reconstitution recommendations can be found summarized in **Table 6** below as well as in the investigator brochure.

Table 6: Investigational Product Properties, Formulation, Storage, Handling, and Reconstitution									
Dosage form/Presentations:									
	Powder/Lyophilisate for solution for infusion								
	1 g Treosulfan per vial								
	5 g Treosulfan per vial								
	Treosulfan is available as a powder or lyophilizate presentation. These 2 presentations are a result of the manufacturing process at different manufacturing sites. It has been confirmed during development that both presentations can be used interchangeably. Therefore, the available presentation has no influence on the safety and efficacy of the product, but only results in a different optical appearance of the drug product. For the 1 g Treosulfan strength, the vial size of the lyophilized product is 30 mL while the vial size of the powder product is 100 mL. This is due to technical reasons. The content of the product is identical.								
Recommended Solvents:									
	Sterile 0.45% sodium chloride solution;								
	Sterile 0.9% sodium chloride solution;								
	Sterile 5% glucose solution;								
	Sterile water for injection								
	Final Treosulfan concentration in the reconstituted solution: 50 mg/mL								
Incompatibilities:									
	In the absence of compatibility studies, the drug product must not be mixed with other medicinal products.								
	Treosulfan should be stored at room temperature (unopened vial). The expiration date is stated on the vial and the outer packaging and is defined in line with the approved shelf life in the respective investigational new drug application/investigational medicinal product dossier.								
	After reconstitution with a recommended solvent, chemical and physical stability has been demonstrated for 3 days at room temperature.								
	From a microbiological point of view, the product should be used immediately after reconstitution unless reconstitution has taken place in controlled and validated aseptic conditions. If not used immediately, in-use storage times and conditions prior to use are the responsibility of the user and may not be longer than 72 hours at room temperature.								
Storage and Handling:									
	If not used immediately store reconstituted solution at room temperature. Do not use if the solution contains a precipitate.								
	Do not refrigerate, as this might cause a precipitate								
	See investigators Brochure (IB) for additional details regarding special precautions for disposal and handling of Treosulfan.								
Instructions for reconstitution of the IMP:									
	Calculate the dose, the total volume of reconstituted Treosulfan solution required, and the number of Treosulfan vials needed.								
	Reconstitute each vial with 0.45% sodium chloride injection, 0.9% sodium chloride injection, 5% glucose injection, or sterile water for injection in its original glass container using volumes described in the table below to obtain a final concentration of approximately 0.05 g/mL of Treosulfan.								
	
  
 Reconstitution Solution Volume	
 
 Strength	Volume	
   
 1 g/vial	20 mL	
 
 5 g/vial	100 mL	
  
	Reconstitution Solution Volume		Strength	Volume	1 g/vial	20 mL	5 g/vial	100 mL
Reconstitution Solution Volume									
Strength	Volume								
1 g/vial	20 mL								
5 g/vial	100 mL								
	Shake the vial(s) to dissolve.								
	Determine the volume of 0.05 g/mL reconstituted solution needed based on the required dose. Reconstitution solutions of Treosulfan may be combined into a larger glass vial, polyvinyl chloride, ethylene vinyl acetate, polyolefin, or polyethylene bag.								

Table 6: Investigational Product Properties, Formulation, Storage, Handling, and Reconstitution	
	To avoid solubility issues, prolonged standing time or slight warming of the reconstituted solution (hand warm) may be useful. Note, a warmer or water bath 25-30°C (not higher) may also be used to warm the 0.45% sodium chloride injection, 0.9% sodium chloride injection, 5% glucose injection, or sterile water for injection (personal communication Medac; also in prior IBs) to be used for reconstitution.
	Inspect the reconstituted solution for discoloration and particulate matter. The reconstituted solution contains approximately 0.05 g/mL of Treosulfan and appears as a clear colorless solution. Solutions showing any sign of precipitation should not be used.
	For preparation of 0.45% sodium chloride solution equivalent volumes of 0.9% sodium chloride solution and water for injections can be mixed.

Voriconazole, posaconazole, itraconazole, and isavuconazole should be discontinued 72 hours prior to the start of conditioning and should not be administered during conditioning due to risk for drug-drug interaction/toxicities. Voriconazole, posaconazole, itraconazole, and isavuconazole may be administered if needed following conditioning.

Treosulfan toxicities are outlined in **Tables 7a (Children) and 7b (Adults)**.

Table 7a: Treosulfan Side Effects in Children		
Very Common (10% or Greater)	Common (1% - 9%)	Uncommon/rare/unknown frequency
Abdominal pain	Abnormal creatinine (kidney function test)	Bleeding in the eye
Abnormal liver tests	Anal inflammation	Blistering of the skin
Anemia (low red blood cell count which can lead to fatigue)	Chills	Burning or prickling sensation on the skin
Diarrhea	Darkening of the skin	Capillary leak syndrome (tissue swelling) which can lead to dangerously low blood pressure
Fever	Difficulty swallowing	Cerebral hemorrhage (bleeding in the brain)
Hair loss	Headache	Constipation
Hepatotoxicity – damage to the liver including abnormal liver tests (not related to venoocclusive disease/sinusoidal obstruction syndrome)	Hives	Decreased appetite
Infections (bacterial, viral, fungal)	Mouth or throat pain	Diaper rash
Itching	Nosebleeds	Dry eyes
Low platelet counts which increases the risk of bleeding	Rash	Edema (swelling due to retention of fluids)
Low white blood cell count which increases the risk of infection	Redness of skin	Enlarged liver
Mucositis/stomatitis (painful inflammation/sores of the lips and lining of the mouth which may cause difficulties eating)	Severe rash with sores and/or peeling of the skin	Excess fluid in body cavity that surrounds the lung
Nausea	Skin pain	Feeling weak or tired
Vomiting (throwing up)		Hand-foot syndrome (redness, swelling, and pain on the palms of the hands and/or soles of the feet)
		Hematuria (blood in urine)
		High blood pressure
		Hypoxia (decrease in the amount of oxygen reaching the tissues)
		Indigestion
		Inflammation of the bladder

Very Common (10% or Greater)	Common (1% - 9%)	Uncommon/rare/unknown frequency
		Less acid than normal in the blood
		Low blood pressure
		Lung failure or pneumonia requiring oxygen therapy or mechanical ventilation
		Pain
		Pain in extremities
		Penile pain
		Pericardial effusion (fluid around the heart)
		Proctitis (rectal inflammation)
		Pulmonary hemorrhage (bleeding within the lungs)
		Seizure
		Severe inflammation of the colon
		Severe loss of kidney function which may require artificial kidney machine
		Skin ulcer
		Swelling of the scrotum
		Treatment-related secondary cancer
		Venoocclusive Disease/Sinusoidal obstruction syndrome (injury to the liver that can result in enlarged liver, liver pain, abdominal fluid, and abnormal liver tests)

Table 4: Treosulfan Side Effects in Adults			
Very Common (10% or Greater)	Common (1% - 9%)	Uncommon (0.1% - 0.9%)	Rare/unknown frequency
Abnormal liver tests	Abdominal/ esophageal pain	Abdominal bloating	Abnormal enzyme test – increased lactate dehydrogenase (LDH)
Anemia (low red blood cell count which can lead to fatigue)	Abnormal heartbeat	Bruising (small red or purple spots on the skin caused by bleeding into the skin)	Abnormal kidney function test
Diarrhea	Back pain	Chest pain	Acidosis (more acid than normal in the blood)
Feeling weak or tired	Bone, joint, or muscle pain	Confusion	Allergic reaction at the site of the drug injection
Fever	Chills	Death of skin tissue	Anal inflammation
Hair loss	Constipation	Dry mouth	Blood clot
Infections (bacterial, viral, fungal)	Decreased appetite	Dry skin	Burning or prickling sensation on the skin
Low platelet counts which increases the risk of bleeding	Difficulty swallowing	Excess fluid in the body cavity that surrounds the lungs	Cardiac arrest
Low white blood cell count which increases the risk of infection	Dizziness (feeling faint, woozy, weak or unsteady)	Glucose intolerance (high or low blood sugar)	Cough
Mucositis/stomatitis (painful inflammation/sores of the lips and/or lining of the mouth that may cause difficulties eating)	Hand-foot syndrome (redness, swelling, and pain on the palms of the hands and/or soles of the feet)	Hiccups	Darkening of the skin
Nausea	Headache	Hyperhidrosis (excessive sweating)	Difficulty speaking
Vomiting (throwing up)	Hematuria (blood in urine)	Liver failure	Dry eyes
	High blood pressure	Lung infection including pneumonia that may require mechanical ventilation	Dysphonia (vocal changes)
	Hypersensitivity (overactive immune system which can	Mouth hemorrhage (excessive bleeding from the mouth)	Enlarged liver

Table 4: Treosulfan Side Effects in Adults			
Very Common (10% or Greater)	Common (1% - 9%)	Uncommon (0.1% - 0.9%)	Rare/unknown frequency
	range from mild to severe)		
	Indigestion	Numbness or pain in hands and feet	Encephalopathy (brain disease that can include temporary or permanent damage)
	Insomnia (trouble sleeping)	Pain	Fainting
	Itching	Pain with urination / urinary tract pain	Feeling cold
	Low blood pressure	Pulmonary Hemorrhage (bleeding within the lungs)	Gastric or intestinal bleeding which can be severe
	Mouth pain	Severe brain bleeding	Heart attack
	Nosebleeds	Severe skin rash with sores and/or peeling of skin	Heart failure
	Pain in extremities	Throat, lung, or mouth inflammation	Hepatotoxicity – damage to the liver including abnormal liver tests (not related to venoocclusive disease / sinusoidal obstruction syndrome)
	Rash	Throat pain	Hypoxia (decrease in the amount of oxygen reaching the tissues)
	Redness of skin	Treatment-related secondary cancer	Inflammation of the bladder
	Sepsis, septic shock (overwhelming blood infection, can be fatal)	Venoocclusive disease / Sinusoidal obstruction syndrome (injury to the liver that can result in enlarged liver, liver pain, abdominal fluid and abnormal liver tests)	Liver pain
	Severe loss of kidney function which may require artificial kidney machine	Vertigo (spinning feeling)	Muscle weakness

Table 4: Treosulfan Side Effects in Adults			
Very Common (10% or Greater)	Common (1% - 9%)	Uncommon (0.1% - 0.9%)	Rare/unknown frequency
	Stomach inflammation		Restlessness or jerking
	Sudden reddening of the face and/or neck		Severe bleeding
	Swelling		Severe inflammation of the colon
	Trouble breathing		Swelling around the heart
	Weight loss or gain		

2.5.6.2.2 Fludarabine

Fludarabine phosphate is commercially available.

Fludarabine (Fludara®) is a purine analog that inhibits lymphocyte proliferation, promotes lymphocyte apoptosis, and is effective in the treatment of lymphoid and myeloid malignancies.⁶³⁻⁶⁵ Fludarabine is phosphorylated intracellularly in several steps to its active form 2-fluoroadenosine arabinoside triphosphate, which acts by inhibiting DNA synthesis.^{63,64} Fludarabine induces immunosuppression and long-lasting lymphopenia, reducing the incidence of GVHD and facilitating engraftment along histocompatibility barriers when used in combination with other chemotherapeutic agents or low-dose TBI.^{64,66} Toxicities related to fludarabine are outlined in **Table 8**.

Table 8: Fludarabine Side Effects		
Common, some may be serious (>20%)	Occasional, some may be serious (4 - <20%)	Rare and serious (3% or fewer)

 • Anemia (low red blood cells) which may require blood transfusions (may lead to tiredness or shortness of breath) • Cough • Feeling of being tired or irritable • Infection, especially when white blood cell count is low • Low platelet counts, which may cause bruising or bleeding • Pain 	
 • Confusion • Chills • Damage to organs (brain, lungs, others) which may cause tiredness, changes in thinking or shortness of breath • Diarrhea (loose stools) • Feeling of "pins and needles" in arms and legs • Nausea, vomiting (throwing up), loss of appetite • Sores in mouth which may cause difficulty swallowing 	
 • Blood in urine • Changes in vision • Coma • Kidney damage, which may require an artificial kidney machine • Liver damage • Seizures

2.5.6.2.3 Thymoglobulin® (Anti-Thymocyte Globulin; Rabbit ATG)

Thymoglobulin® is commercially available.

Thymoglobulin® (Anti-Human Thymocyte Globulin; ATG; Sangstat Medical Corp., Fremont, CA) is an immunosuppressant which alters the function of or eliminates T-cells and NK cells.

Rabbit anti-thymocyte globulin (Thymoglobulin®) is a polyclonal immunoglobulin mixture (IgM/IgG) raised in rabbits against human T thymocytes which reduces all circulating lymphocytes or lymphocyte subsets. ATG is used in preparation for HCT, as immunosuppressive therapy in aplastic anemia, and for GVHD treatment.

Thymoglobulin® is provided in 25mg vials by Sangstat. Each thymoglobulin® vial should be reconstituted with 5ml sterile water to a concentration of 5mg/ml. Further dilute dose in D5W or NS to a final concentration of 0.5 mg/mL. Diluted drug should be used immediately.

Thymoglobulin® should be administered alone and not run piggyback with any other solution. A 0.22 micron in-line filter should be used during administration via central line or high flow vein. The first and second dose of Thymoglobulin® should be infused over 6 hours, and the subsequent dose may be infused over 4 hours if there are no clinical concerns. Toxicities related to thymoglobulin are outlined in **Table 9**.

Table 9: Thymoglobulin® (rATG) Side Effects		
Likely (May happen in more than 20% of patients)	Less Likely (May happen in 20% or fewer patients, but more than 2%)	Rare, but Serious (May happen in 2% or fewer patients)

 • General pain, could also include joint and muscle pain • Headache • High or low potassium levels in the blood • High blood pressure • Fast heart rate • Infection, which may cause fever and chills • Low red blood cell counts, which may cause tiredness or may require blood transfusions • Low white blood cells, which may cause increased infections and slower wound healing • Low platelet levels, which may cause bruising, bleeding • Nausea, vomiting, diarrhea, constipation, stomach pain 	
 • Acid/base imbalances in the blood • Cough • Feeling anxious • Feeling tired • High fat levels in the blood • High phosphate levels in the blood • Rash, itching • Reaction to the medication infusion, which may include itching, fever, chills, low blood pressure and problems breathing • Sweating • Swelling of the body • Post-transplant lymphoproliferative disease (PTLD) often caused by Epstein-Barr Virus (EBV). This can lead to fatal lymphoma. • Problems sleeping 	
 • Allergic reaction which may cause rash, low blood pressure, wheezing, shortness of breath, swelling of the face or throat

2.5.6.2.4 Tacrolimus

Tacrolimus is a calcineurin inhibitor used for immunosuppression. Toxicities related to tacrolimus are outlined in **Table 10**.

Table 10: Tacrolimus Toxicities		
Common, some may be serious (>20%)	Occasional, some may be serious (4 - <20%)	Rare and serious (3% or fewer)

 • Abnormal body movement, including tremors • Change of laboratory values that may need corrected: high sugar, high lipids, altered electrolytes • Constipation, diarrhea, nausea, vomiting, reflux, lack of desire to eat • Difficulty sleeping • Dizziness • Feeling of "pins and needles" in arms and legs • Headache • High blood pressure which may cause dizziness, chest pain • Itching, rash • Kidney damage which may cause swelling, may require an artificial kidney machine • Low platelet levels, which may cause bruising, bleeding • Liver damage • Low red blood cell counts, which may cause tiredness, or may require blood transfusions • Low white blood cell counts, which may lead to infection • Swelling of the body 	
 • A new cancer resulting from treatment of earlier cancer • A tear or a hole in the bowels which may cause belly pain or that may require surgery • Allergic reaction which may cause rash, low blood pressure, wheezing, shortness of breath, swelling of the face or throat • Change in the heart rhythm, abnormal heartbeat, or heart stops beating • Damage to lungs, which may cause shortness of breath, fluid around lungs • Damage to brain, which may cause headache, seizure, blindness • Heart attack or failure which may cause chest pain, swelling of ankles, and tiredness 	
 • Damage to small blood vessels with resulting small blood clots and possible organ damage.

Occasionally the kidney damage is severe enough to require the use of intravenous fluids or even an artificial kidney machine. If the patient’s kidney function is poor prior to transplant, there is an increased risk that the patient may develop kidney failure necessitating an artificial kidney machine, possibly permanently.

2.5.6.2.5 Methotrexate

Methotrexate (MTX) is an antimetabolite used for immunosuppression. Toxicities related to methotrexate are outlined in **Table 11**.

Table 11: Methotrexate Side Effects		
Common, some may be serious (>20%)	Occasional, some may be serious (4 - <20%)	Rare and serious (3% or fewer)

 • Increased risk of sunburn, rash 	
 • Anemia from low red blood cell count which may cause tiredness, or may require transfusion 	
 • A new cancer resulting from treatment of an earlier cancer

 • Nausea, vomiting, loss of appetite • Sores in mouth which may cause difficulty swallowing 	
 • Blood clot which may cause swelling, pain, shortness of breath • Bruising, bleeding from low platelet count • Diarrhea, sores in the gastrointestinal tract • Fluid around heart • Hair loss • Hepatitis or damage to the liver which may cause yellowing of eyes and skin, generalized swelling • Infection, especially when white blood cell count is low • Kidney damage 	
 • Internal bleeding which may cause stomach pain, black tarry stool, blood in vomit • Scarring of the lungs which may cause shortness of breath, confusion • Severe skin rash with blisters and peeling which can involve mouth and other parts of the body

In the setting of renal or hepatic dysfunction, where there is impaired clearance of the medication, methotrexate may contribute to delayed neutrophil engraftment. Methotrexate may also cause an elevation in serum transaminase.

2.6 Study Conduct

This study will be conducted in accordance with the protocol, the BMT CTN MOP (located on the BMT CTN Website), and the following:

- a. Consensus ethical principles derived from international guidelines including the Declaration of Helsinki
- b. Applicable ICH Good Clinical Practice (GCP) Guidelines
- c. Applicable laws and regulations

The National Marrow Donor Program (NMDP) single Institutional Review Board (IRB) of Record will oversee this study and conduct the study-specific reviews as required by federal regulations and per the NMDP IRB Standard Operating Procedures (SOPs).

Site personnel will enter data in the electronic case report form (eCRF) in Advantage eClinical as described in the BMT CTN 1904 Forms Guide. Source documentation should be made available for monitoring visits, audits, and regulatory inspections as described in the BMT CTN MOP.

Participating Principal Investigators (PIs) bear ultimate responsibility for training of site staff as

well as the scientific, technical, and administrative aspects of conduct of the protocol, even when certain tasks have been delegated to coinvestigators, sub-investigators, or staff. The PIs have a responsibility to protect the rights and welfare of patients and comply with all requirements regarding the clinical obligations and all other pertinent requirements in 21 CFR part 312. In addition to following applicable federal, state, and local regulations, investigators are expected to follow ethical principles and standards and receive training in GCP every three years and human subjects training within the past 3 years and thereafter as per institutional requirements.

CHAPTER 3

3 STUDY ENDPOINTS AND DEFINITIONS

3.1 Primary Endpoint

3.1.1 Graft-Versus Host-Disease (GVHD), Event-Free-Survival (EFS)

The primary endpoint is the incidence of 1-year GVHD free, EFS (GEFS). An event is defined as death due to any cause, graft rejection/failure, or 2nd HCT whichever occurs first. Grade III-IV acute GVHD and chronic GVHD (using NIH consensus criteria) requiring systemic immune suppression will be considered in this estimate.^{61,62}

3.2 Secondary Endpoints

3.2.1 Overall Survival

Overall survival will be estimated at day 100, 6 months, and 1 year after HCT.

3.2.2 Event-Free Survival

Event-free survival will be estimated at 12 months after HCT. Grade III-IV acute GVHD and chronic GVHD requiring systemic immune suppression will be considered in this estimate.^{61,62} An event is defined as death due to any cause, primary or secondary graft failure/rejection, or 2nd HCT whichever occurs first.

Primary Graft Failure/Rejection: defined as never achieving ANC $\geq 500/\mu\text{L}$ or never achieving $\geq 5\%$ donor myeloid chimerism assessed by peripheral blood chimerism assays by day +42 post-HCT. Second infusion of hematopoietic cells is also considered indicative of primary graft failure by day +42 post-HCT.

Secondary Graft Failure/Rejection: defined as $< 5\%$ donor myeloid chimerism in peripheral blood beyond day +42 post-HCT in patients with prior documentation of hematopoietic recovery with $\geq 5\%$ donor cells by day +42 post-HCT. Second infusion of hematopoietic cells is also considered indicative of secondary graft failure.

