1 BACKGROUND AND STUDY RATIONALE

1.1 Objectives

The primary objective of this phase II study is to determine the 1-year graft-versus-host-disease (GVHD)-free, event-free survival (EFS) in patients with bone marrow failure diseases (BMFD) undergoing HLA-matched related, matched unrelated, or single HLA-class 1 allele or HLA-DQB1 antigen or allele mismatched unrelated hematopoietic cell transplantation (HCT) using Treosulfan-based conditioning. An event will be defined as death due to any cause, graft rejection/failure, or 2nd HCT whichever occurs first. GVHD will be defined as grade III-IV acute GVHD or chronic GVHD (using NIH consensus criteria) requiring systemic immune suppression.

Secondary objectives are to determine:

- 1 Overall survival at day 100, 6 months, and 1-year post-HCT.
- 2 EFS at 1-year post-HCT. An event will be defined as death due to any cause, graft rejection/failure, or 2nd HCT.
- 3 Neutrophil recovery at day 42 and platelet recovery at day 100 post-HCT.
- 4 Donor chimerism (CD3 and myeloid) at day 28, 100, and 1-year post-HCT.
- 5 Primary graft failure/rejection at day 42 and secondary graft failure/rejection post-HCT.
- 6 Grade II-IV and grade III-IV GVHD at day 100 and chronic GVHD (using NIH consensus criteria) requiring systemic immune suppression at 1-year post-HCT.
- 7 Incidence of grade 3-5 toxicities at day 30 and day 100 post-HCT.
- 8 Incidence of grade 2-3 systemic infections at 6-months post-HCT.
- 9 Incidence of EBV-reactivation requiring therapy and the incidence of EBV-associated lymphoproliferative disorder by day 180 post-HCT.
- 10 Incidence of CMV reactivation requiring therapy by day 180 post-HCT.

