2.2.2 Objectives

Primary Objective:

The primary objective of this phase II study is to assess the 1-year GVHD-free, EFS in patients with BMFD undergoing HCT using Treosulfan-based conditioning. An event will be defined as death due to any cause, graft rejection/failure, or 2nd HCT whichever occurs first. GVHD will be defined as grade III-IV acute GVHD or chronic GVHD (using NIH consensus criteria) requiring systemic immune suppression.

Secondary Objectives:

Secondary objectives will be to determine:

1. Overall survival at day 100, 6 months, and 1-year post-HCT.
2. EFS at 1-year post-HCT
 - a. An event will be defined as death due to any cause, graft rejection/failure, or 2nd HCT.
3. Neutrophil recovery at day 42 and platelet recovery at day 100 post-HCT.
4. Donor chimerism (CD3 and myeloid) at day 28, 100, and 1-year post-HCT.
5. Primary graft failure/rejection at day 42 and secondary graft failure/rejection post-HCT.
6. Incidence of grade II-IV and grade III-IV GVHD at day 100 and chronic GVHD requiring systemic immune suppression at 1-year post-HCT.
7. Acute GVHD will be defined as grade II-IV and grade III-IV.⁶¹
8. Chronic GVHD will be defined as chronic GVHD (using NIH consensus criteria) requiring systemic immune suppression.⁶²
9. Incidence of grade 3-5 toxicities at day 30 and day 100 post-HCT.
10. Incidence of grade 2-3 systemic infections by day 180 post-HCT.
11. Incidence of EBV-reactivation requiring therapy and the incidence of EBV-associated lymphoproliferative disorder by day 180 post-HCT.
12. Incidence of CMV reactivation requiring therapy by day 180 post-HCT.

Exploratory Objectives:

1. Treosulfan Pharmacokinetic Studies: Treosulfan PK characteristics to determine the optimal dose of Treosulfan and evaluate whether the exposure to Treosulfan determined by area under the curve (AUC) for patients with BMFD impacts engraftment, transplant-related mortality, and overall and event-free survival.
2. Biological Studies: Collect blood and marrow samples (cells, DNA, serum) and establish fibroblast cell cultures as a source of germline DNA to investigate: 1) somatic mutations, 2) T cell phenotypes, and 3) cytokine levels.
3. Mutational Testing: Collect peripheral blood on patients who lack a known genetic mutation responsible for their bone marrow failure phenotype in order to perform whole exome or whole genome sequencing with the goal of identifying new mutations for patients with BMFD.

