5.5 Analysis Populations and General Analysis Guidelines

5.5.1 Primary Analysis Population

All patients conditioned with a Treosulfan-containing regimen will be included in the primary analysis population. Time to event analyses will start at initiation of conditioning (day -6 of transplant). Analyses for the primary endpoint, all secondary endpoints, and safety endpoints, will use the primary analysis population. The primary analysis will occur once all patients have been followed for 12 months, Endpoint Review Committee adjudication completed, and data is locked.

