5.6 Analysis of Primary Endpoint

The probability of GEFS at 1 year will be estimated using the Kaplan-Meier method, along with 95% confidence intervals computed using a complementary log-log transformation.

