5.7.2 GVHD-Free, Event-Free Survival

GVHD-free, event-free survival will be estimated at 1 year using the Kaplan-Meier method, along with 95% confidence intervals computed using a complementary log-log transformation.

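### Event-free survival, secondary objective 2, has a contradictory definition in Section 3.2.2, and its place in the analysis section (5.7.2) repeats the primary GEFS analysis

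*Protocol*

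**What the plan says.** - **Objectives.** The Synopsis and Sections 1.1 and 2.2.2 each list 1-year EFS as the second secondary objective, apart from the primary GEFS objective. Section 1.1 reads "EFS at 1-year post-HCT. An event will be defined as death due to any cause, graft rejection/failure, or 2nd HCT". Section 2.2.2 gives the same three events: "An event will be defined as death due to any cause, graft rejection/failure, or 2nd HCT". Neither includes GVHD.
- **Primary endpoint, Section 3.1.1.** After the same kind of three-event list, GVHD is brought in by one sentence: "Grade III-IV acute GVHD and chronic GVHD (using NIH consensus criteria) requiring systemic immune suppression will be considered in this estimate".
- **Secondary endpoint, Section 3.2.2 (headed Event-Free Survival).** It contains "Grade III-IV acute GVHD and chronic GVHD requiring systemic immune suppression will be considered in this estimate". Its event list nevertheless omits GVHD: "An event is defined as death due to any cause, primary or secondary graft failure/rejection, or 2nd HCT whichever occurs first".
- **Primary analysis, Section 5.6.** "The probability of GEFS at 1 year will be estimated using the Kaplan-Meier method", with a 95% interval by complementary log-log transformation.
- **Secondary analyses, Section 5.7.** The item after overall survival is 5.7.2, titled GVHD-Free, Event-Free Survival: "GVHD-free, event-free survival will be estimated at 1 year using the Kaplan-Meier method", with the same interval method.
- **Population, Section 5.5.1.** "Analyses for the primary endpoint, all secondary endpoints, and safety endpoints, will use the primary analysis population".

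**The concern.** EFS and GEFS answer different questions. EFS shows whether the conditioning achieves survival with a lasting graft, which is the rationale argued in Section 1.2. GEFS adds the burden of GVHD. Reporting both lets a reader see how much of any shortfall is due to GVHD. EFS is also quoted in the background from the pilot and the registry, and it is one of the outcomes that the exploratory pharmacokinetic objective relates to treosulfan exposure.

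As drafted, the definition in 3.2.2 conflicts with the objective, and the analysis section names the primary endpoint where EFS should stand. Secondary objective 2 could then go unanswered. Alternatively, the EFS definition might be settled only after outcomes are known, in an unblinded single-arm trial.

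**Working it through.** **1. Definitions side by side**

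| Section | Endpoint named | Event list | GVHD sentence |
|---|---|---|---|
| 1.1, 2.2.2 (secondary objective 2) | EFS | death, graft rejection/failure, second transplant | none |
| 3.1.1 | GEFS | the same three events | yes |
| 3.2.2 | EFS | the same three events, with primary and secondary graft failure named | yes |

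GVHD is in neither event list in Chapter 3. In 3.1.1 it enters only through the added sentence. If that sentence adds GVHD in 3.1.1, the near-identical sentence in 3.2.2 adds it there too. If it adds nothing, the primary endpoint as defined in 3.1.1 loses its GVHD component. So 3.2.2 cannot be squared with the objective by calling the sentence inert.

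**2. Analyses side by side**

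| Section | Quantity | Estimator | Horizon | Interval | Population |
|---|---|---|---|---|---|
| 5.6 | GEFS | Kaplan-Meier | 1 year | complementary log-log | primary analysis population |
| 5.7.2 | GEFS | Kaplan-Meier | 1 year | complementary log-log | primary analysis population |

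Every column agrees, so the two results would be the same number with the same interval. The other parts of 5.7 cover overall survival, hematologic recovery, chimerism, acute and chronic GVHD, toxicities and infections. None covers EFS without GVHD, and neither does 5.8. The table of contents carries the same title for 5.7.2.

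**3. Direction of the difference**

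The GEFS events are the EFS events plus GVHD. Each patient's first GEFS event therefore comes no later than the first EFS event, and the true EFS probability is at least the GEFS probability. With complete follow-up, which Section 5.2 nearly expects, the same holds for the observed proportions.

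**4. How far apart the two can be, from the protocol's own background**

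- Pilot, 23 patients (Sections 1.2 and 1.3.4): 2-year EFS 96%, 1-year GEFS 87%. These match 22/23 = 95.7% and 20/23 = 87.0%, counts inferred here and not stated in the protocol. Difference: 95.7 − 87.0 = 8.7 points.
- Registry, 92 patients (Section 1.3.2): 1-year EFS 81.4% overall; GVHD-free EFS 65% with serotherapy and 62.4% without. Differences: 81.4 − 65 = 16.4 and 81.4 − 62.4 = 19.0 points.

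Expected events at n=40, as 40 × (1 − rate):

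| Assumed rates | EFS events | GEFS events |
|---|---|---|
| Pilot | 40 × 0.04 = 1.6 | 40 × 0.13 = 5.2 |
| Registry | 40 × 0.186 = 7.4 | 40 × 0.35 = 14.0 to 40 × 0.376 = 15.0 |

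These comparisons are illustrative only:
- The pilot EFS is a 2-year figure and its GEFS a 1-year figure.
- The event list that Section 1.3.4 gives for the pilot GEFS includes disease recurrence, which this trial does not count.
- The registry's GVHD component is extensive chronic GVHD, a different definition from this trial's.
- The registry EFS is for all patients, while its GVHD-free figures are for serotherapy subgroups.

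**5. What is not affected**

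Table 15 concerns GEFS only. Exact Clopper-Pearson intervals reproduce it:

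| Observed | Exact 95% CI | Table 15 |
|---|---|---|
| 38/40 | 83.1–99.4% | 83–99% |
| 36/40 | 76.3–97.2% | 76–97% |
| 34/40 | 70.2–94.3% | 70–94% |
| 32/40 | 64.4–91.0% | 64–91% |

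None of these depends on EFS.

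**The case against.** **The intent is recoverable.** EFS is listed three times as a separate objective, twice with an event list free of GVHD, and the event list in 3.2.2 agrees with it. A reader might infer that 3.2.2 simply redefines EFS as GEFS. That is too strong, because the section contradicts itself. The objection stands as to certainty, but a contradictory definition still needs resolving, and 5.7.2 is wrong on either reading.

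**The output would not be mislabelled.** A reader might infer that the trial will publish a figure called EFS that contains GVHD events and looks falsely poor beside the pilot and registry. Section 5.7.2 is titled and worded as GEFS, so following it gives a duplicate GEFS and no EFS. A mislabelled EFS would come only from the literal reading of 3.2.2. This objection stands.

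**The background gaps are not a bias.** A reader might take 9 to 19 points as the amount by which EFS would be understated. The mismatches listed in the working rule that out. What survives is the direction of the difference and the fact that it can be material.

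**A separate statistical analysis plan may put it right.** Possibly. But Section 5.5.3 ties each endpoint's analysis to 5.6 to 5.8, and 5.8.1 defers only the laboratory-sample endpoints. The protocol states wrong content here; it does not leave a detail open. A later plan that corrected it would contradict the protocol.

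**Little depends on it.** Section 5.7 calls the secondary analyses primarily descriptive, and EFS is not tested. This lowers the severity without removing the fault.

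**Conclusion.** The point holds at moderate severity. Section 3.2.2 contradicts secondary objective 2 and its own event list, and 5.7.2 repeats the primary analysis in the place of the EFS analysis. If 5.6 to 5.8 are followed literally, the primary result appears twice and EFS as the objective defines it is not estimated.

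The size of the effect in this trial is unknown. EFS will be equal to or higher than GEFS, given that the EFS events are a subset of the GEFS events and follow-up is near complete. A reader might also infer that EFS is lost to the trial. It is not: GEFS already requires its component events, so EFS can be computed from the same records. The primary endpoint, the sample size of 40, Table 15 and the monitoring of day-100 mortality and graft failure do not change.

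**What to change.** 1. In Section 3.2.2, delete the sentence on acute and chronic GVHD and keep the event list that follows it.
2. Retitle Section 5.7.2 *Event-Free Survival* and rewrite it as the 1-year Kaplan-Meier estimate of EFS. The events are death from any cause, primary or secondary graft failure or rejection, or a second transplant, whichever comes first. Give a 95% confidence interval by complementary log-log transformation, in the primary analysis population. GEFS stays in 5.6 only, and the table of contents is updated to match.

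The cost is two wording edits, best made before the primary analysis. They need no new data and change neither the sample size nor the treatment or monitoring of patients.
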